9.4.1.3 IMPUTATION OF MISSING DATA AND SENSITIVITY ANALYSES

All attempts will be made to minimize missing data. However, if any subjects in the ITT population have missing primary endpoints, five (5) multiple imputations will be used for the analyses. This consists of imputing values for each missing value as a set (generating 5-sets), analyzing the results for each set, and then pooling the results. The Primary Effectiveness Endpoint is continuous, so the imputation method will be a multiple linear regression using treatment assignment and baseline characteristics.

Protocol #: D00232675

08 September 2021

A sensitivity analysis of the Primary Effectiveness Endpoint will be conducted as a tipping-point analysis, to examine the impact of missing data. It will only be conducted if the hypothesis test passes (i.e., rejects H_0). We will start by assuming that all missing Primary Effectiveness Endpoints have values indicating the inferiority of *Vibe SF* strategy, and if the Primary Effectiveness Hypothesis is not passed, we will change one missing endpoint to a difference of 0 until the hypothesis passes. This will enable determination of the amount of missing data that would alter the final result on the primary effectiveness endpoint.

If the hypothesis test of the Primary Effectiveness Endpoint does not pass, the hypothesis test will be repeated using only those subjects without major protocol violations, i.e., the mITT population. This test is for SPONSOR's information only, and will not be used to support the study objective.

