9.2 SAMPLE SIZE DETERMINATION

The sample size was estimated for the Primary Effectiveness Objective; that is the only objective with a hypothesis test. The sample size of 24 was estimated using Pass 2019 and the following parameters:

Parameter	Value
Difference between HCP fit and Vibe SF scores (δ) 
 • EC(benefit) • BN(benefit) • RV(benefit) 	
 • $\delta = \Delta EC(benefit)_{HCP\ fit fit} - \Delta EC(benefit)_{SF} = 0$ • $\delta = \Delta BN(benefit)_{HCP\ fit fit} - \Delta BN(benefit)_{SF} = 0$ • $\delta = \Delta RV(benefit)_{HCP\ fit fit} - \Delta RV(benefit)_{SF} = 0$
SD (σ) of scores within a fitting strategy and for the difference between Vibe SF and HCP fit, assuming independence ($\sqrt{2\sigma^2}$)* 
 • EC(benefit) • BN(benefit) • RV(benefit) 	
 • $\sigma = 24.3; \sigma_{DIFF} = 34.4$ • $\sigma = 25.6; \sigma_{DIFF} = 36.1$ • $\sigma = 25.5; \sigma_{DIFF} = 36.2$ 
(Leohler & et al, 2017)

Non-inferiority margins (NIMs) 
 • EC(benefit) • BN(benefit) • RV(benefit) 	
 • EC(benefit) = 26 • BN(benefit) = 27 • RV(benefit) = 28 
(Cox & Alexander, 1995)

Power	90% on all 3 tests simultaneously, or 96.5% on each individually ($.965^3 = .90$)
Alpha	5% on all 3 tests simultaneously
Test Type	Paired t-Tests for Non-Inferiority

* The variance of the difference of two means is used, not 4 means, even though this is the difference of differences. The reason is that the baseline value (unaided) from which benefit is measured is the same for the SF period and the HCP fit period. Therefore, the difference of differences reduces to the difference between the aided SF score and aided HCP fit score.

** All 3 tests must simultaneously have $p < .05$

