9.3 POPULATIONS FOR ANALYSES

The following populations will be used in the analyses of the Primary and Secondary endpoints in this study.

ITT Population: The intent to treat (ITT) population includes all subjects who received at least one hearing aid fitting strategy (*Vibe SF* or HCP fit) to evaluate. This population will be used for the Primary Objective hypothesis test. Missing values will be handled as described in Section 9.1.2.

mITT Population: The modified intent to treat (mITT) population includes all subjects in ITT population who have an endpoint for the analysis in question. The mITT population will be used for the analysis of the Secondary Objectives. No imputation of missing values will be done for these endpoints.

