9.4.1.2 CONTROL OF TYPE 1 ERROR

All hypothesis tests (of which there is only one compound test in this study, and that is for the Primary Effectiveness Objective) will be conducted at $\alpha=0.05$. Non-inferiority tests (the type of test in this study) are by nature one-tailed. The Primary hypothesis test will be conducted in 3 parts, as described in Section 9.1.1. To control Type 1 error associated with multiple tests, all 3 tests for the Primary Objective must have a p-value of 0.05 or smaller simultaneously.

Although the Secondary Objectives do not include any hypothesis testing, they will not be analyzed or reported unless the primary hypotheses pass (reject all 3 H_0 s).

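### In the cross-over, missing primary endpoints are imputed without the subject's own observed score from the other period, which biases the comparison if Period 1-related drop-out differs between the two orders

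*Combined protocol and SAP*

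**What the plan says.** Section 9.4.1.3 applies when ITT subjects lack a primary endpoint: "five (5) multiple imputations will be used for the analyses", and "the imputation method will be a multiple linear regression using treatment assignment and baseline characteristics". Section 9.3 defines ITT as everyone who received at least one fitting strategy and adds: "This population will be used for the Primary Objective hypothesis test". A subject with only one completed period is therefore in the primary test.

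That subject's first score exists. Section 8.1.4 collects the aided APHAB for the Field Test 1 device at Visit 2, and Section 7.2 keeps data collected before withdrawal. The cross-over analysis in Section 9.4.2.1 is a repeated-measures comparison of the two devices.

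The plan does not settle which quantity is imputed. The synopsis and Section 3 define the endpoint as each subject's HCP-minus-SF difference, and the tipping-point rule in 9.4.1.3 resets a missing endpoint to a zero difference. Treatment as a predictor, and the period-level model in 9.4.2.1, fit more naturally with imputing the missing period score.

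**The concern.** In a within-subject comparison, the subject's score on the other device is likely to be a strong predictor of the missing one. If leaving depends on a poor Period 1 result, the data are missing at random when that result is in the imputation model, but not when it is left out. The stated model gives a poor Period 1 scorer an average second score, or an average difference, and so discards the reason that the subject left.

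Drop-out that differs by order is plausible here. Section 6.3 says the field tests cannot be blinded. Under Section 8.1.3, HCP-fit subjects can be invited for in-person fine-tuning, while staff will not answer questions about fitting or using Vibe SF. The imputed values enter the primary ITT test directly, so bias towards Vibe SF would raise the chance of a false non-inferiority claim on a subscale.

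**Working it through.** **Inputs from the documents.** Section 9.2: EC SD 24.3 per strategy; SD of the difference 34.4 (√2 × 24.3 = 34.4); EC margin 26; zero within-subject correlation, for want of information; up to 15% drop-out, 24 + 4 = 28 (4/28 = 14.3%). Alpha is "5% on all 3 tests simultaneously", one-sided by Section 9.4.1.2. Section 9.4.1.3: 5 imputations.

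**Assumptions.** Within-subject correlation ρ = 0, 0.5 or 0.8; 14 subjects per order; drop-out after Period 1, strongly favouring low Period 1 benefit. The documents give no drop-out mechanism.

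**The plan's own figure.** Power = P(T > t) for a noncentral t with n − 1 degrees of freedom and noncentrality margin × √n / SD of the difference. For EC: 26 × √23 / 34.4 = 3.62, power 0.96892 at n = 23, as stated. The other five tabulated powers also reproduce.

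**Simulation at the EC margin.** 6000 trials per cell, proper regression imputation, Rubin pooling with small-sample degrees of freedom, one-sided 95% bound. Monte Carlo error is at most about 0.5 percentage points. Each cell shows Type 1 error, with bias in points of HCP minus SF; negative favours Vibe SF.

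| Imputed quantity | Low scorers lost from | ρ = 0 | ρ = 0.5 | ρ = 0.8 |
|---|---|---|---|---|
| Period score, stated model | HCP-first | 4.2% (+0.08) | 7.2% (−2.01) | 9.2% (−3.17) |
| Period score, stated model | SF-first | 4.8% (+0.03) | 1.8% (+1.97) | 0.3% (+3.21) |
| Period score, stated model | both equally | 4.7% (+0.08) | 3.7% (0.00) | 2.8% (−0.03) |
| Difference, stated model | HCP-first | 1.0% (+4.88) | 1.7% (+2.45) | 2.1% (+0.97) |
| Difference, stated model | SF-first | 14.9% (−4.81) | 10.5% (−2.38) | 7.3% (−0.89) |
| Difference, stated model | both equally | 4.4% (−0.04) | 4.3% (−0.09) | 4.7% (−0.01) |
| Period score, other-period score added | HCP-first | 4.0% (+0.12) | 4.0% (−0.03) | 4.8% (+0.03) |
| Period score, other-period score added | SF-first | 5.3% (−0.01) | 5.0% (+0.07) | 4.4% (+0.07) |

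**Why the pattern makes sense.** When period scores are imputed, the information thrown away is proportional to ρ: 2.01/0.5 = 4.0 and 3.17/0.8 = 4.0. When differences are imputed, it is proportional to 1 − ρ: 4.88/1 = 4.9, 2.45/0.5 = 4.9 and 0.97/0.2 = 4.9. So the first reading is harmless at ρ = 0 and the second is worst there.

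**Milder cases.** With weaker selection and HCP-first loss (period score), the error is 4.0%, 5.4% and 5.6% at the three correlations. With two lost instead of four under strong selection, it is 4.2%, 5.6% and 6.5%. For SF-first loss with the difference imputed, the corresponding figures are 10.2%, 7.1%, 5.9% and 10.8%, 8.2%, 6.5%. With the other-period score added to the period-score model, every pattern stays between 3.7% and 5.6%, with bias within about 0.2 points.

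**Cross-check.** Two further simulations of the HCP-first, period-score case at ρ = 0.5 and 0.7 gave 7.3% and 8.9%, and 6.6% and 8.8%. For SF-first loss with the difference imputed, one of these gave 9-16%.

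**Precision under random loss** (period scores imputed, unaided-aided correlation assumed 0.3). At ρ = 0.5 the mean SE is 5.20 with the stated model and 4.97 with the other-period score: 5.20/4.97 = 1.05. At ρ = 0.7 it is 4.46 against 3.86: 4.46/3.86 = 1.16, about 15%. Near ρ = 0 there is no gain.

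**Number of imputations.** Taking missing information at about 14%, five imputations are 1/(1 + 0.14/5) = 97% efficient.

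**The case against.** The 7-9% figure stacks several conditions: all four losses in one order, strong selection of low scorers, and correlation of 0.5 or more. At the plan's zero correlation, imputing period scores produces no inflation, and the mirror pattern makes the test conservative. The biases of 2.01 and 3.17 points are 8% and 12% of the 26-point margin, so they matter mainly when the true difference is near the margin. The tipping-point analysis runs exactly when the test passes and starts from values unfavourable to Vibe SF. All of this stands, and it limits the size of the problem.

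It does not remove the problem. Zero correlation was used for want of information, and on the difference reading it is the worst case. The tipping-point analysis may expose a fragile result, but it does not change the primary decision.

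A reader might go further in three ways that the documents do not support:

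- That any drop-out related to Period 1 biases the result. It must differ by order; equal dependence gave no bias and error below 5%.
- That the trial's Type 1 error is 7-9% or more. These are single-subscale rates. All three subscales must pass, so the overall error is lower unless the other two are well inside their margins.
- That the plan vouches for this rule as conservative. The remarks on conservatism in Section 9.4.2.1 concern the harmonic-mean p-value, not imputation.

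**Conclusion.** The concern holds for the cross-over analysis only. The omission is plain in the text, and following the rule as written gives a biased primary comparison when Period 1-dependent drop-out differs by order. The direction depends on an unstated choice between imputing the period score and imputing the difference.

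In the extreme case, per-subscale Type 1 error is about 7-9% (period score, HCP-first loss, correlation 0.5-0.8) or about 7-16% (difference, SF-first loss, even near correlation 0). Opposite patterns are conservative. Under random loss with period scores imputed, the SE is about 5% larger than needed at correlation 0.5 and about 15% larger at 0.7. The correlation and the drop-out mechanism are assumptions, so these figures show what is possible and are not forecasts. The plan should be changed because the correction is cheap and removes the bias in every pattern simulated.

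**What to change.** In Section 9.4.1.3, for the cross-over analysis, state that the missing period score is imputed. Use a model with the subject's observed other-period score on that subscale, the unaided score, treatment and period/order. Alternatively, fit a likelihood mixed model with a subject effect to all observed period scores. More than five imputations is an optional refinement. Section 9.3 also points to Section 9.1.2 for missing data and should point to 9.4.1.3.

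The cost is SAP wording and slightly more analysis work, with no new data, and a slightly larger SE if the within-subject correlation is near 0. The change cannot help subjects who leave before Visit 2, because they have no aided score to use.

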9.4.1.4 RANDOMIZATION AND BLINDING

At the time of the visit on which the subject is provided with his/her first hearing aid, he/she will be randomized to either: *Vibe SF* First/HCP fit Second or to HCP fit First/*Vibe SF* Second. A computer-generated pseudo-random-number list will be used for assigning the treatment order. Assignments will be made either by sealed envelope or provided real-time on the sponsor's EDC website on a protected page.

9.4.2 ANALYSIS OF THE PRIMARY EFFECTIVENESS ENDPOINT

The mechanism for validating the *Vibe SF* strategy will be the comparison of subject's hearing aid benefit as measured by the change from each of the three APHAB communication subscales (EC, BN, RV) benefit score (benefit score = unaided – aided) when the hearing aids are HCP fit compared to when it is *Vibe SF* by the subject.

There are 3 APHAB communication subscales that contribute to the perceived benefit (response condition), and each subscale benefit (EC, BN, RV) must simultaneously demonstrate the non-inferiority of *Vibe SF* strategy to HCP fit strategy. Note that higher means are worse (i.e., higher differences mean that *Vibe SF* strategy performed worse).

- H_0 EC(benefit): $\Delta EC(benefit)_{HCP \text{ fit}} - \Delta EC(benefit)_{SF} \geq 26$ vs
 H_a EC(benefit): $\Delta EC(benefit)_{HCP \text{ fit}} - \Delta EC(benefit)_{SF} < 26$
- H_0 BN(benefit): $\Delta BN(benefit)_{HCP \text{ fit}} - \Delta BN(benefit)_{SF} \geq 27$ vs
 H_a BN(benefit): $\Delta BN(benefit)_{HCP \text{ fit}} - \Delta BN(benefit)_{SF} < 27$
- H_0 RV(benefit): $\Delta RV(benefit)_{HCP \text{ fit}} - \Delta RV(benefit)_{SF} \geq 28$ vs
 H_a RV(benefit): $\Delta RV(benefit)_{HCP \text{ fit}} - \Delta RV(benefit)_{SF} < 28$

Protocol #: D00232675

08 September 2021

These are non-inferiority tests comparing the subject's perceived hearing aid benefit as measured by the difference in each of the three APHAB communication benefit subscales when the hearing aid is HCP fit compared to when it is *Vibe SF* by the subject. The NIM depends on the communication benefit subscale, according to Cox (1995), and these are the minimum clinically important differences on each of the three communication benefit subscales.

Note that because of the adaptive design which entails possibly moving from a cross-over design to a parallel-arm design, the analysis methods must differ slightly. Section 9.4.2.1 describes the analysis we will use for a cross-over design. Section 9.4.2.2 describes how we will use the cross-over analysis for the interim analysis to determine if we must adapt the design. Section 9.4.2.3 describes the analysis we will use for a parallel-arm design if we change the design.

9.4.2.2 INTERIM ANALYSIS OF CROSS-OVER DESIGN FOR DETERMINATION OF DESIGN APPLICATION

An interim analysis will be conducted to determine if the design will be changed from a cross-over to a parallel-arm design. The analysis will be conducted by an independent statistical group so that no information about the effects of fitting (SF vs HCP FIT) will be known to Sponsor. A nuisance parameter will be estimated and tested for significance to decide whether to change the design.

[figure not shown]
The analysis will be conducted as follows.

Each communication benefit subscale will be analyzed using a repeated-measures analysis of variance (rm-ANOVA) in which the repeated (within) factors are order (HCP fit first or SF first) and treatment (HCP fit or SF); there are no between-group factors. The interaction term, order x treatment, will be included to determine whether it is necessary to change from a cross-over design to a parallel-arm design. This is the nuisance factor that is the crux of the adaptation. The presence of an interaction term means that the difference in benefit (i.e., the treatment effect) differs by order. In this case, we cannot combine the estimate of HCP FIT-first benefit with HCP fit-second, and similarly for SF-first and second. Here is the visual representation of the effects in the following Figures a, b and c:

[figure not shown]
a) Treatment (TX) Effect

b) TX, Order Effects

c) TX, Order, Interaction Effects

HCPF = HCP fit

Figure (a) shows an effect of treatment only. The score with SF, averaged over SF First and SF Second, is different from the average score of HCP fit. The scores for SF are the same for both orders, and that is also true for HCP fit, so there is no order effect. The difference between SF and HCP fit is the same for both orders, so there is no interaction effect.

Figure (b) shows an effect of treatment and of order. The average SF score is lower than the average HCP fit score, and the averages are lower when SF is first than when HCP fit is first. However, the difference between SF and HCP fit is the *same regardless of order*, which means there is no interaction effect. So, in spite of the order effect, it is possible to *estimate the difference between treatments and to test for the non-inferiority of SF to HCP fit*.

Figure (c) shows an effect of treatment and order, and also an interaction effect. The interaction effect occurs because the difference between treatments is *not* the same with both orders. Compare this to Figure (b), in which the difference *is* the same. In this case, the test for non-inferiority of SF to HCP fit

Protocol #: D00232675

08 September 2021

must be done on SF First and HCP fit First separately because non-inferiority might be true in one case and not in the other.

It is important to note that it is not the order effect, but the interaction effect, that makes it impossible to do a non-inferiority test. The interaction term will be tested by combining the p-values from the 3 scales. The method WHM, shown in Section 9.4.2.1, will be used here, but in this case, it will be the interaction term p-values that are combined. The combined p-value will be compared to $\alpha=0.10$; if the null hypothesis of no interaction is rejected in favor of the hypothesis of an interaction, we will switch to the parallel-arm design.

If the design is switched to parallel-arm, then subjects who have not crossed over will have only one treatment, and subjects who have crossed over will have only their first treatment used in the analysis of the parallel-arm data. See Section 9.4.2.3.

9.4.2.3 ANALYSIS OF PARALLEL-ARM DESIGN DATA

Each communication benefit subscale will be analyzed using a t-test of the benefit with SF (as described previously, the difference between baseline and SF score) versus the benefit with HCP fit (the difference between baseline and HCP fit score). ***The p-values for all 3 communication subscales must be 0.05 or smaller in order for the global hypothesis test to pass (reject the global null of inferiority).***

Because Sponsor would like to report a global p-value for these tests, the 3 p-values will be combined into a single value using the method of WHM as described as in Section 9.4.2.1. The p-values cannot be assumed to be independent because the data are from the same set of subjects, and it is therefore likely that the benefit on the EC score is correlated with the benefit on the RV score, etc.

Descriptive statistics for the treatment groups for each of the three communication benefit subscales, EC(benefit), RV(benefit), BN(benefit), at each time point will also be reported.

9.4.3 ANALYSIS OF THE SECONDARY ENDPOINTS

Descriptive statistics will be reported on each endpoint by fitting strategy and overall, according to the list in Section 9.4.1.1. In addition, some endpoints require more detailed description. Additional descriptive statistics that will be reported are listed with the endpoints.

EMA Scores: Descriptive statistics of the scores will be reported by fitting strategy and measurement time for each real-life condition.

QuickSIN Scores: Descriptive statistics of the scores will be reported by fitting strategy and measurement time.

SSQ-12 Scores: Descriptive statistics of the scores will be reported by fitting strategy and measurement time for each subscale.

Protocol #: D00232675

08 September 2021

Gain Selection: Descriptive statistics of the probe-mic REM will be reported by fitting strategy and measurement time.

Fitting Preference: Descriptive statistics of the scores will be reported by fitting strategy and measurement time.

9.4.4 SAFETY ANALYSES

It is very unlikely that any device-related adverse events (ADEs) will be reported during this NSR device study. However, those that are reported will be tabulated by severity (mild-moderate-severe), seriousness (serious or non-serious) and relatedness (related, not related).

9.4.5 BASELINE DESCRIPTIVE STATISTICS

Descriptive statistics of patient demographics and baseline hearing status will be tabulated. No comparisons will be made because the same subjects serve as *Vibe SF* and HCP fit strategy groups in this cross-over study. The statistics that will be tabulated for each variable are listed by variable type in Section 9.4.1.1.

9.4.6 PLANNED INTERIM ANALYSES

See Section 9.4.2.2. We will conduct an interim analysis using a nuisance parameter to decide if the design of the study will be changed from a cross-over design to a parallel-arm design.

9.4.7 SUB-GROUP ANALYSES

This study does not include any sub-group analyses.

9.4.8 TABULATION OF INDIVIDUAL SUBJECT DATA

Data listings by subject will be provided to regulatory agencies.

10 SUPPORTING DOCUMENTATION AND OPERATIONAL CONSIDERATIONS

10.1 REGULATORY, ETHICAL, AND STUDY OVERSIGHT CONSIDERATIONS

10.1.1 INFORMED CONSENT PROCESS

10.1.1.1 CONSENT/ASSENT AND OTHER INFORMATIONAL DOCUMENTS PROVIDED TO SUBJECTS

Protocol #: D00232675

08 September 2021

The responsible investigator at each site ensures that approval of advertisements used to recruit subjects and of the Patient Information / Informed consent form, from an appropriately constituted IRB, is sought for the clinical investigation. The decision of the IRB concerning the conduct of the clinical investigation will be made in writing to the Sponsor and Investigator before commencement of this clinical investigation. The clinical investigation can only begin once approval has been received. Any additional requirements imposed shall be implemented.

Consent forms, including all items as per ISO1455, describing in detail the study intervention, study procedures, and risks are given to the subject and written documentation of informed consent is required prior to starting intervention/administering study intervention. The following consent materials are submitted with this protocol:

- Patient Information Sheet
- Informed Consent Form

The above listed documents are provided separately.

